The Implementation of Cognitive Stimulation Therapy Hong Kong Version (CST-HK) for Promoting Cognitive Functioning and Psychosocial Well-being of People with Dementia

Research Protocol 12 February 2018

Investigators

[name] Assistant [name] of Social Work and Social Administration The University of Hong Kong Email: [contact] [contact]

[name] Physiotherapist Elderly Service Department Hong Kong Young Women's Christian Association

[name] Clinical Associate [name] of Psychiatry The University of Hong Kong

[name] PhD Candidate Department of Social Work and Social Administration The University of Hong Kong

Background

Dementia is a group of disorders characterized by cognitive impairments that affect a person's everyday functional ability, causing disability and poor quality of life. It affects 46.8 million people worldwide in 2015, and the number is expected to reach 74.7 million in 2030 and 131.5 million in 2050 (Prince et al., 2015). The World Health Organization has announced it as a public health priority since 2012 (World Health Organization, 2012). In Hong Kong, the number of people with dementia is projected to increase two-fold from 103,433 in 2009 to 332,688 in 2039 (Yu et al., 2012). There is currently no cure for the condition.

Non-pharmacological interventions such as cognitive training, cognitive rehabilitation, and cognitive stimulation aim at slowing down the cognitive decline experienced by a person with dementia (Bahar-Fuchs, Clare, & Woods, 2013). Cognitive stimulation involves a range of group activities and discussions to enhance general cognitive and social functioning. A meta-analysis of 15 studies with a total of 718 persons with dementia showed evidence of benefits of cognitive stimulation on cognitive function, quality of life, and self-reported well-being of the people with dementia (Orrell et al., 2017). The benefits appeared to add on to medication effects (Aguirre, Woods, Spector, & Orrell, 2013). The clinical improvements in verbal and visual memory, orientation, and auditory comprehension after cognitive stimulation appeared to be able to translate into improvements in real world activity (Hall, Orrell, Stott, & Spector, 2013), as seen in enhancement of the communication and social interaction of persons with dementia (Woods, Aguirre, Spector, & Orrell, 2012).

In view of the current evidence, cognitive stimulation is recommended by the National Institute for Health and Clinical Excellence and the Alzheimer's Disease International as an evidencebased, non-pharmacological intervention to be offered to all people with mild-to-moderate dementia (National Institute for Health and Clinical Excellence [NICE], 2007; Prince, Bryce, & Ferri, 2011). A standard protocol of cognitive stimulation therapy with evidence is a 7-week intervention developed by Spector and her colleagues (Spector et al., 2003). It is a series of standardized, well-structured stimulating activities, implemented in a sensitive, respectful and person-centered manner. Group CST typically involves 14 sessions of 45-minute group activities that required cognitive processing delivered over a 7-week period (2 sessions per week, with approximately 45 mins per session) (Aimee Spector et al., 2003). The group size was standardized to be 6 to 8 persons (Orrell et al., 2017). People with dementia would participate in each of the 14 designated theme activities during each session. The activities aimed at stimulating and engaging persons with dementia in an active way, and providing an optimal learning environment and the positive social benefits of group therapy (National Institute for Health and Clinical Excellence [NICE], 2007). Cognitive stimulation therapy can be delivered by non-specialist healthcare workers with minimum training (Khan, Corbett, & Ballard, 2014; Paddick, 2015; Aimee Spector et al., 2003). This allows CST to be used in low-resource environment (Paddick, 2015). Manuals in different languages had been published for the group leaders to follow. Due to this advantage of high reproducibility with high quality evidence support, CST was widely adopted in over 20 countries (Orrell et al., 2017).

In Hong Kong, there is currently no recommendations or routine provision of cognitive stimulation. In 2015, the standard group CST protocol was culturally adapted for and tested in Chinese people with dementia in Hong Kong (CST-HK) (Wong et al., 2017). The observed improvements in cognitive outcome was in line with that of overseas studies (Hall et al., 2013; Aimee Spector, Orrell, & Woods, 2010). The protocol appeared to be feasible and acceptable

to Hong Kong Chinese, with high attendance rate (92%) and low attrition rate (13%). Cultural issues identified in the pilot have been published and recommendations were made in adapting the protocol to the Hong Kong cultural settings (Wong et al., 2017). A Hong Kong Chinese version of the manual for CST group leaders has been published in 2017 (Spector, Thorgrimsen, Woods, & Orrell, 2017).

This healthcare promotion project aims to enhance the quality of life and cognition of people with mild-to-moderate cognitive impairment through the use of CST-HK delivered by trained non-professional group leaders. As part of project evaluation, we aim to test the effectiveness of CST-HK compared with a wait-list control group who will receive care as usual during the waiting period.

Research Objectives

The research aims to investigate the effectiveness of CST-HK among people with mild-tomoderate cognitive impairment in Hong Kong in a larger scale across service settings. We also aim to explore the effectiveness of CST-HK delivered by non-professional staff, as a possible solution to address the shortage of specialized healthcare manpower and increasing demands of non-pharmacological interventions for people with dementia.

Hypotheses

We hypothesized that, compared with the wait-list control group, the group who have received a 7-week (14-session) CST-HK intervention delivered by trained non-professional staff will show greater improvement or maintenance of (1) quality of life; and (2) cognitive performance.

Research Design

This is a cluster randomized wait-list control study.

Study Sample

A total of 128 older persons with mild to moderate cognitive impairment will be recruited from nine service units of Hong Kong Young Women's Christian Association, including two residential care units and seven community care units. This sample size is calculated based on the primary outcomes of quality of life and cognitive function. Repeated measure analysis of variance (ANOVA), between factors will be used. Assuming a medium effect size (f = 0.25), 80% power and 5% significance level, with two groups and two time points (calculated using G*Power 3.1.9.2), a total of 98 participants are required. We propose a sample size of 128 to accommodate for a 30% attrition rate.

Inclusion and exclusion criteria are:

- A clinical diagnosis of mild-to-moderate dementia, or a cognitive assessment result suggestive of mild-to-moderate cognitive impairment;
- Be able to communicate and understand Cantonese;
- Be able to hear and see well enough to participate in the cognitive stimulation activities;
- No major illness that would affect participation (including clinically significant depressive symptoms or acute psychotic disorders);
- No behavioural problems (e.g., aggression, inappropriate sexual behaviors) or psychotic symptoms (e.g., hallucination, delusion) that would interfere with participation in the intervention;
- A caregiver who is able to give joint informed consent.

Intervention and Procedures

A briefing session will be provided to participants and their family caregivers by the staff of Hong Kong Young Women's Christian Association for recruitment. Upon giving written consent, participants will be randomized into intervention group (n=64) or waitlist control group (n=64) in groups of eight. Two randomization lists will be generated by HKU researchers, one each for residential care units and community care units. Hong Kong Young Women's Christian Association will be informed about the group allocation upon successful recruitment of eight eligible participants. The intervention group will receive the14-session group CST-HK (45 minutes per session, two times a week, for 7 weeks in total) provided by trained facilitators. The wait-list control group will receive usual care in the service units they are attach to and will start their CST-HK programme after an 8-week delay.

A total of 40 CST-HK facilitators without specialized healthcare background will be recruited by Hong Kong Young Women's Christian Association. They are required to attend two 4-hour workshops to acquire the knowledge and skills for delivering CST-HK. The knowledge and skills include the guiding principles, and the theme of each training session. After the workshops, the facilitators will be designated to nine elderly service units mentioned above and practice their learnt knowledge and skills in delivering CST-HK under the supervision of experienced CST-HK interventionists with specialized healthcare background in Hong Kong Young Women's Christian Association. At the end of the practicum, the trainees will be evaluated to ensure the fidelity of CST-HK.

The person with dementia and their caregivers will undergo an interview at study baseline and 7 weeks. A service assistant blind to the group allocation will conduct the interviews. The interview will last for approximately 45 minutes for the person with dementia and the caregiver, respectively. A post-intervention assessment will be conducted in the wait-list control group upon completion of the delayed intervention.

Measurements for Primary Outcomes

The primary outcome of CST-HK, quality of life, will be measured using the Quality of Life in Alzheimer's Disease scale (Chan, Chu, Lee, Li, & Yu, 2011; Logsdon, Gibbons, McCurry, & Teri, 2002). Self-rating of the persons with dementia would be used in this study using the patient version of this tool.

Cognitive function will be measured using the Alzheimer's Disease Assessment Scale-Cognitive Subscale test (Chu et al., 2000). No deterioration in cognition is defined as a change in the score of ≥ 0 point in ADAS-Cog, and clinically meaningful improvement a change in score of ≥ 4 points, in the post-intervention assessment compared with baseline score.

Data Analysis

Intention-to-treat analysis will be conducted. For the main outcome measures of quality of life and cognition, ANOVA will be used to assess changes from baseline to 7 weeks after between the intervention group and the wait-list control group. Further analysis will be conducted by ANCOVA controlling for baseline differences in age, gender, education level, type of care setting, AChEI use (using random effects) and baseline cognition and quality of life. As a sensitivity analysis, we will also conduct exploratory analysis including the post-intervention data from the wait-list control group.

References

- Chan, I. W. P., Chu, L. W., Lee, P. W., Li, S. W., & Yu, K. K. (2011). Effects of cognitive function and depressive mood on the quality of life in Chinese Alzheimer's disease patients in Hong Kong. *Geriatrics & gerontology international*, 11(1), 69-76.

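### The 98-participant calculation is for the group main effect averaged over baseline and week 7, so the stated 80% power does not belong to the planned test of change

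*Combined protocol and SAP*

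**What the plan says.** The Study Sample section names the test behind the sample size: "Repeated measure analysis of variance (ANOVA), between factors will be used". The inputs are "Assuming a medium effect size (f = 0.25"), "80% power and 5% significance level", "with two groups and two time points (calculated using G*Power 3.1.9.2"). The result is that "a total of 98 participants are required", followed by "We propose a sample size of 128 to accommodate for a 30% attrition rate".

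The Hypotheses section predicts that the intervention group "will show greater improvement or maintenance of (1) quality of life; and (2) cognitive performance", relative to the wait-list group. The Data Analysis section says "ANOVA will be used to assess changes from baseline to 7 weeks after between the intervention group and the wait-list control group". ANCOVA with baseline cognition and quality of life among the covariates appears only as further analysis.

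The protocol gives no correlation between visits, no SD, no effect in scale points, and no calculation for a test of change.

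**The concern.** With two arms and two visits, a repeated-measures ANOVA offers two tests that involve the arms. The between-factors test (group main effect) compares the arms on each participant's average of baseline and week 7. The group-by-time interaction compares them on the change between the visits. The hypothesis and the analysis section describe the second; the sample size was computed for the first.

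The between-factors test suits a difference present at both visits. Here baseline precedes treatment and allocation is random, so the expected baseline difference is zero and any effect appears only at week 7. Averaging in the baseline halves it.

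Two things follow. A reader cannot tell from the protocol what power the planned test has. And because the sample-size paragraph says the between-factors test will be used, an analyst who followed it could report an F-test that dilutes a real benefit on both primary outcomes.

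**Working it through.** **Inputs from the protocol.** f = 0.25, 80% power, 5% significance, k = 2 groups, m = 2 visits, N = 98, recruitment of 128, 30% attrition, equal arms (64 and 64).

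**Assumptions.** The correlation between visits, ρ, is not stated; 0.5 is used first and then varied. SDs are taken as equal at both visits. Participants are treated as independent, as in the protocol's own calculation. Power comes from the noncentral F distribution with noncentrality λ.

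**1. Reproducing 98.** For the between-factors test, λ = f²·N·m / (1 + (m − 1)ρ), with 1 and N − 2 degrees of freedom.
- N = 98: λ = 0.0625 × 98 × 2 / 1.5 = 8.17, power 80.8%.
- N = 96: λ = 0.0625 × 96 × 2 / 1.5 = 8.00, power 79.9%.

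So 98 is the smallest even N at ρ = 0.5. The same test needs 84 at ρ = 0.3 and 110 at ρ = 0.7.

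**2. Ruling out the interaction test as the source.** Here λ = f²·N·m / (1 − ρ). At f = 0.25 and ρ = 0.5 the answer is 34 (λ = 0.0625 × 34 × 2 / 0.5 = 8.5). Over ρ from 0 to 0.9 it never exceeds 66, so it cannot have produced 98.

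**3. What f = 0.25 implies at week 7.** For two groups, f = 0.25 is a 0.5 SD difference. In the between-factors test that difference is on the average of the two visits. With a baseline difference of 0 and a week-7 difference of d, the average difference is (0 + d)/2. Setting d/2 = 0.5 gives d = 1.0 SD at week 7. Conversely, a medium week-7 difference of d = 0.5 corresponds to f = d/4 = 0.125, both for the main effect and for the interaction.

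**4. Power for a 0.5 SD week-7 difference, 98 completers, ρ = 0.5.**
- Between factors: λ = 0.015625 × 98 × 2 / 1.5 = 2.04, power 29%.
- Change score: standardised effect 0.5 / √(2(1 − ρ)) = 0.5, λ = 98 × 0.25 / 4 = 6.13, power 69%.
- Baseline-adjusted ANCOVA: standardised effect 0.5 / √(1 − ρ²) = 0.577, λ = 98 × 0.333 / 4 = 8.17, power 81%.

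The change test reaches 80% at 128 completers (λ = 128 × 0.25 / 4 = 8.0). That is the whole recruited sample with no attrition. After 30% loss, 128 × 0.7 = 89.6, about 90 remain; change-test power is then 65% (λ = 90 × 0.25 / 4 = 5.63).

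**5. Dependence on the correlation** (0.5 SD at week 7, 98 completers).

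| ρ | Between factors | Change | ANCOVA | Total N for 80%, change test |
|---|---|---|---|---|
| 0.3 | 33% | 54% | 73% | 178 |
| 0.5 | 29% | 69% | 81% | 128 |
| 0.6 | 28% | 78% | 86% | 104 |
| 0.7 | 26% | 89% | 93% | 78 |
| 0.8 | 25% | 97% | 98% | 54 |

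**6. The alternative reading.** If f = 0.25 is entered as the interaction effect itself, it means a 1.0 SD difference in change (f = d/4). Power at 98 is then at least 98.5% for ρ of 0.3 or more.

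**The case against.** The strongest reply is that no direction of harm has been shown. The protocol never says that f = 0.25 means a 0.5 SD difference at week 7 only. On the interaction reading power is very high, and even on the week-7 reading the change test passes 80% once the correlation reaches about 0.62. This stands: the mismatch alone does not show that the trial is underpowered, and the 69% depends on the reading and on the assumed correlation. It does not rescue the stated 80%, which still belongs to another test.

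Second, baseline-adjusted ANCOVA for a 0.5 SD week-7 difference at correlation 0.5 also needs 98. That is true but coincidental: 1 − ρ² and (1 + ρ)/2 both equal 0.75 at ρ = 0.5. The match fails elsewhere (73% at ρ = 0.3), the protocol does not derive 98 this way, and ANCOVA is not its main analysis. It does mean that, if ANCOVA became primary, 98 completers could be defended at that correlation, before clustering.

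Third, the between-factors phrase may be only the software option, since the Data Analysis section clearly speaks of change. That is plausible, and it makes reporting of the diluted test less likely. But the phrase says the test will be used, so the two sections still need reconciling.

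Finally, all these powers treat participants as independent, although allocation is in groups of eight. That is correct, and clustering would lower each of them.

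**Conclusion.** The concern holds. The figure of 98 is the between-factors result, reproduced exactly at an assumed correlation of 0.5, while the hypothesis and the main analysis concern change from baseline. The 80% therefore does not describe the planned test. In the powered test, f = 0.25 corresponds to a 1.0 SD difference at week 7, twice what "medium" conventionally suggests for a two-group comparison.

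How far the true power departs from 80% cannot be settled from the protocol: it depends on the unstated correlation and on what effect f = 0.25 was meant to represent. The defect is a power statement attached to the wrong test. It must be corrected, but it is not proof that the trial is too small.

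**What to change.** In the Study Sample section, replace the between-factors calculation with one for the test that will be used: either the difference in change or, preferably, the week-7 difference adjusted for baseline, which has the higher power at every correlation tabulated above. State the assumed week-7 difference (in scale points and SD, for each primary outcome) and the baseline to week-7 correlation, with a range. Then restate the power of 128 recruits after attrition and a design effect for the groups of eight. In the Data Analysis section, state that the primary test is the group-by-time or baseline-adjusted contrast and not the group main effect.

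The correction is to text only and does not itself change enrolment. The restated power may be less favourable. For example, keeping the change test, a 0.5 SD effect and correlation 0.5, 80% power needs 128 completers, or 128 / 0.7 ≈ 183 recruits before any allowance for clustering. The sponsor would then have to accept the lower power, justify a higher correlation, make ANCOVA primary, or recruit more.

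### A sample of 128 does not cover 30% attrition: about 90 would remain against the 98 required, and 128 tolerates at most 23.4% loss

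*Combined protocol and SAP*

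**What the plan says.** The Study Sample section sets out the calculation in consecutive sentences. The test is named first: "Repeated measure analysis of variance (ANOVA), between factors will be used". The inputs follow: "Assuming a medium effect size (f = 0.25), 80% power and 5% significance level, with two groups and two time points". The result is that "a total of 98 participants are required", and the enrolment target comes next: "We propose a sample size of 128 to accommodate for a 30% attrition rate".

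Intervention and Procedures splits that target equally: "participants will be randomized into intervention group (n=64) or waitlist control group (n=64) in groups of eight".

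The only other attrition figure is in the Background, where the Hong Kong pilot is reported to have lost 13%. The protocol gives no other definition of attrition and no formula for the step from 98 to 128.

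**The concern.** An attrition rate is a share of the people enrolled. For the sentence to be true, 70% of 128 must be at least 98, and it is not.

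This sentence is the only justification given for the enrolment target. A reader would conclude that the trial can lose 30% of its participants and still have the number it says it needs for 80% power. Anyone monitoring retention against that allowance would regard losses between 23.4% and 30% as planned for, although the trial would already have fallen below 98.

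The intention-to-treat statement in Data Analysis does not close the gap. The main analysis is described thus: "ANOVA will be used to assess changes from baseline to 7 weeks". A participant with no 7-week score has no observed change, and no method for missing 7-week outcomes is given.

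**Working it through.** **Inputs from the protocol**

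- Required total 98, planned total 128, attrition 30% (Study Sample)
- 64 per arm (Intervention and Procedures)
- Pilot attrition 13% (Background)
- f = 0.25, 5% significance, 80% power, two groups, two time points, between factors (Study Sample)

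**Input not in the protocol**

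- The correlation ρ between the two time points. It is needed only for the power figures in steps 1 and 5.

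**1. Reproducing the 98.** For the between-factors test with two measures, the noncentrality is λ = N × f² × 2/(1 + ρ), with 1 and N − 2 degrees of freedom. Assume ρ = 0.5.

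- N = 98: λ = 98 × 0.0625 × 2/1.5 = 8.17, power 80.8%
- N = 96: λ = 8.00, power 79.9%

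So 98 is the smallest even total that reaches 80%. Any ρ from 0.498 to 0.529 gives the same answer. A ρ of 0.45 would give 94 and a ρ of 0.55 would give 100.

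**2. Testing the attrition statement.**

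- Remaining in total: 128 × (1 − 0.30) = 89.6, about 90. Shortfall against 98: about 8.
- Remaining per arm: 64 × 0.70 = 44.8, about 45. Needed per arm: 98/2 = 49.
- Recruits needed to keep 98 after 30% loss: 98/0.70 = 140. Shortfall against 128: 12.

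**3. What 128 does cover.**

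- Largest loss in total: 128 − 98 = 30, and 30/128 = 23.4%.
- Largest loss per arm: 64 − 49 = 15, and 15/64 = 23.4%.
- At the pilot's 13%: 128 × 0.87 = 111.4, about 111 remaining, above 98.

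**4. Where 128 may have come from.** The 30 extra recruits are 30/98 = 30.6% of the number required. Adding 30% to the requirement gives 98 × 1.30 = 127.4, which rounds up to 128. This is an inference, since no formula is printed; 128 is also 16 whole groups of eight. Steps 2 and 3 hold however 128 was reached.

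**5. Effect on power.** Same formula, ρ = 0.5 assumed:

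| N | Situation | Power |
|---|---|---|
| 128 | no loss | 90.0% |
| 111 | 13% loss | 85.4% |
| 98 | 23.4% loss | 80.8% |
| 90 | 30% loss | 77.3% |

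At N = 90, power runs from 77.4% to 76.5% over the correlations that reproduce 98 (0.498 to 0.529), and from 78.7% to 75.9% over the wider range 0.45 to 0.55. None of these figures allows for clustering, and none is the power of the change-from-baseline analysis described in Data Analysis.

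**The case against.** The strongest reply is that little turns on this.

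- **Pilot attrition.** The only observed attrition figure in the documents is 13%, which leaves about 111 and meets 98 with room to spare. This stands, and it limits the consequence. It does not make the sentence true, because the plan chose 30% as its allowance and justified its target by it.
- **Small power loss.** If 30% were lost, power would be about 77%, which is 2.7 points below the 80% target and 3.5 points below the 80.8% at N = 98. This also stands.
- **A margin on 98.** The 30% may have been meant as an addition to the 98. That probably explains the figure, but the text calls it an attrition rate, and 30 losses out of 128 are 23.4%.
- **Intention-to-treat.** It could be said that everyone randomized is analysed, so losses do not count. Without a stated method for missing outcomes this does not help, and the plan's own inflation of 98 assumes that losses reduce the usable number.

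Two cautions about the correction are fair. The 98 itself shows no allowance for the cluster design, so a corrected sentence should not present it as sufficient beyond the calculation that produced it. And if enrolment were raised instead, whole groups of eight with equal arms would take the total to 144 (72 per arm), not 140. That is not proposed here.

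**Conclusion.** The concern holds. With 30% attrition, 128 recruits yield about 90 completers, about 8 fewer than the 98 the plan requires (about 45 against 49 per arm). The attrition that 128 can absorb is 23.4%. This rests on three printed numbers (98, 128 and 30%) and on reading attrition as a share of those enrolled; it does not depend on the unstated correlation.

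The error is certain and its effect is bounded. It matters only if losses exceed 23.4%. At 30%, power for the between-factors calculation would be about 77%, subject to the assumed correlation of 0.5 and before clustering. The sentence should be corrected. Whether 98 is adequate for a cluster-randomized design is a separate question that this check does not address.

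**What to change.** Replace the last sentence of the sample size paragraph with wording such as: *A sample of 128 accommodates up to about 23% attrition (30 participants, 15 per arm) while retaining the 98 given by the calculation above; at the 13% attrition seen in the pilot, about 111 would remain.*

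If the sponsor prefers to keep 30% as the planning figure, the text should say that about 90 completers (about 45 per arm) are then expected, below the 98 needed for 80% power. That would be accurate but would leave the gap open, so restating the allowance as about 23% is better.

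No power figure needs to be printed. If one is given for 90, it should read about 77% for the between-factors calculation, with the assumed correlation of 0.5 stated, labelled as before clustering and not as the power of the change-from-baseline analysis.

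The cost is one sentence. Enrolment, design and analysis stay as they are, and the stated allowance falls from 30% to about 23%.

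### Do the two ADAS-Cog cut-points need a stated sign, visit and analysis before the plan can be followed?

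*Combined protocol and SAP*

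**What the plan says.** Under Measurements for Primary Outcomes, cognition is measured by ADAS-Cog and two cut-points are added. The lower one reads "No deterioration in cognition is defined as a change in the score of ≥ 0 point in ADAS-Cog". The higher one, given in the same sentence, reads "clinically meaningful improvement a change in score of ≥ 4 points, in the post-intervention assessment compared with baseline score". Neither the direction of the scale nor the order of subtraction is stated.

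Under Intervention and Procedures, participants and caregivers in both arms "will undergo an interview at study baseline and 7 weeks". The wait-list arm "will start their CST-HK programme after an 8-week delay", and the protocol adds: "A post-intervention assessment will be conducted in the wait-list control group upon completion of the delayed intervention".

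Under Data Analysis, for both main outcomes "ANOVA will be used to assess changes from baseline to 7 weeks after between the intervention group and the wait-list control group". ANCOVA with baseline covariates follows. The wait-list arm's later data appear once, in an exploratory sensitivity analysis "including the post-intervention data from the wait-list control group". The cut-points do not appear in that section. Under Hypotheses, the intervention group is expected to show "greater improvement or maintenance of (1) quality of life; and (2) cognitive performance".

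**The concern.** Three items that a programmer needs are not written down.

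- **Sign.** If a higher ADAS-Cog score means worse cognition (an assumption, since the protocol does not say), subtracting baseline from follow-up would label decliners as improvers.
- **Visit.** The term post-intervention occurs three times. Outside the definition it refers both times to wait-list data collected after that arm's own CST-HK. Read literally, a wait-list participant would be classified after treatment, and a comparison of arms would set treated against treated.
- **Use.** The cut-points sit under the primary outcomes and echo the hypothesis, yet no comparison, status or rule for missing scores is given.

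At stake would be a response rate whose sign, visit and test were chosen after the data were seen.

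**Working it through.** **1. Sign.** Let c be the change as the protocol intends it. The set c ≥ 0 is labelled as no deterioration, and the set c ≥ 4 as improvement. If positive c meant worsening, c ≥ 4 would be a worsening of at least 4 points carrying the label of improvement, which contradicts the label. So positive c means improvement, whichever way the scale runs. The order of subtraction then follows from the scoring of the instrument: baseline minus follow-up if higher is worse, the reverse if higher is better. The analyst has that information when scoring the test.

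**2. Visit.** Set the statements on timing side by side:

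| Item | Intervention arm | Wait-list arm |
|---|---|---|
| Interviews in both arms | baseline, 7 weeks | baseline, 7 weeks |
| End of own CST-HK | week 7 | about 8 + 7 = week 15 (delay counted from baseline) |
| Main comparison (Data Analysis) | baseline to 7 weeks | baseline to 7 weeks |
| Use of later wait-list data | not applicable | exploratory only |

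In the intervention arm the two descriptions coincide. In the wait-list arm they differ, but the only between-arm contrast planned for cognition is at 7 weeks. Any between-arm use of the cut-points would therefore take week 7. If they are used instead to describe each person's response to CST-HK, the later visit is the proper one for the wait-list arm, and no randomised contrast is involved.

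**3. Role in the planned inference.** The sample size under Study Sample rests on f = 0.25, 80% power, 5% significance, two groups and two time points, for the between-factors test. With the correlation ρ assumed to be 0.5 (it is not stated) and m = 2:

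λ = N f² m / (1 + (m − 1)ρ) = 98 × 0.0625 × 2 / 1.5 = 8.17, with 1 and 96 degrees of freedom.

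Power is 0.808 at N = 98 and 0.799 at N = 96, so the protocol's 98 is reproduced. No response rate enters. ANOVA and ANCOVA likewise work on the scores.

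**4. How far the readings differ.** As an illustration only, assume that change in the direction of improvement is normal with SD 6, control mean 0 and intervention mean 3 (0.5 SD). The rate of reaching 4 points is 1 − Φ((4 − μ)/6), or 1 − Φ((4 + μ)/6) with the sign reversed.

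| Reading | Intervention | Wait-list | Difference |
|---|---|---|---|
| Week 7, positive = improvement | 1 − Φ(1/6) = 43.4% | 1 − Φ(4/6) = 25.2% | +18.2 points |
| Wait-list read after its own course, equal benefit | 43.4% | 43.4% | 0 |
| Week 7, sign reversed | 1 − Φ(7/6) = 12.2% | 25.2% | −13.0 points |

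In all three rows the difference in mean change at week 7 is the same 3 points, so the planned analysis gives the same answer. Step 2 excludes the second row as a between-arm comparison, and step 1 excludes the third. A reversed sign would also show itself, because the arm with the better mean change would have the lower response rate.

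The rates should not be taken as the protocol's own. Its f concerns group means averaged over both time points. With equal baselines, a 0.5 SD difference in that average means 1.0 SD at week 7. At ρ = 0.5 the SD of change equals the SD of the score, because √(2(1 − 0.5)) = 1. The intervention mean would then be 6 and its rate 1 − Φ(−2/6) = 63%, against 25%.

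**The case for a change.** The strongest case for a change runs as follows. A follow-up score compared with baseline reads most naturally as follow-up minus baseline. The protocol's own vocabulary points to the later wait-list visit. The cut-points stand under the primary outcomes, and maintenance of cognition has no other operational definition. The commitment to intention-to-treat does not say how someone without a 7-week score is classified. Response rates are easily quoted from a service evaluation, and clarifying them would take only a few sentences.

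Part of this stands. The wording is loose, the later visit does share the name, and no rule is given for a missing category. A report that quotes these rates should say which direction and which visit it used.

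The rest does not carry. The natural word order yields to the labels, which admit only one sign. The shared name yields to Data Analysis, which fixes the between-arm interval and assigns the later wait-list data to exploratory work. The hypothesis needs no cut-point: a difference in mean change covers both an intervention arm that improves and one that holds steady while the control arm declines. The protocol does not plan a test on the cut-points, so there is no planned result that an unwritten choice could move.

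**Conclusion.** No change to the plan is called for. This is missing detail that analysts would fill in one sensible way: positive change means improvement, and any comparison of arms uses the 7-week interview. The effect is nil on the 98 required and 128 proposed participants, and nil on the planned ANOVA and ANCOVA. Deleting the cut-points altogether would alter no planned result, which shows how little depends on them.

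The conclusion rests on three assumptions: the labels mean what they say, a between-arm use follows the interval in Data Analysis, and the cut-points stay descriptive. If a report presented a test of response rates as a planned primary result, that test would lie outside this plan and should be read as post hoc.
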